4.0 Eligibility Criteria

4.1 Inclusion Criteria

- Male and female, between the ages of 18 to 35 years.
- Required to be a competitive recreational or college athlete and have at least 1-2 years of cycling or biking experience.
- Body Mass Index (BMI) of 18.5 to 28 kg/m²

- Considered “moderately to highly active” by the International Physical Activity Questionnaire (IPAQ).
- Have clinically treated mild to moderate persistent asthma and/or exercise-induced bronchoconstriction (EIB), with a resting forced expiratory volume in 1 second (FEV₁) > 65% of predicted.
- A ≥ 10% drop in FEV₁ after eucapnic voluntary hyperpnea (EVH).
- Prescribed short-acting β_2 -agonists (SABAs) by a physician.
- Comfortable not taking SABA before experimental visits.

4.2 Exclusion Criteria

- History of smoking or recreational smoking, cardiovascular disease, renal disease, neurological disease, and metabolic disease.
- Currently taking asthma maintenance medications (e.g., corticosteroids and leukotriene modifiers)
- Any injuries in the past 6 months.
- Taking SSRI's (antidepressants and anxiety medication), ADD/ADHD medication, and chronically consume pain medication (Aleve, Tylenol, CBD, etc).
- Resting blood pressure of > 130mmHg systolic or 90 mmHg diastolic.
- Resting Pulse rate of > 100 bpm.
- Regularly consuming fish oil supplements or eating more than one fish meal per week

5.0 Study Design

The study design is a randomized, single-blind parallel group study. Participants will complete a formal screening visit and five experimental visits. The five experimental visits will occur each day ± 1 hour, at least 24 hours apart, and ≥ 2 hours postprandial.

The participants were required to visit the laboratory 5 times to complete the experimental tests. *Visit 1.* Participants underwent pulmonary function testing (PFT) and completed a eucapnic voluntary hyperpnea (EVH) challenge to diagnose EIB. *Visit 2.* Participants completed an incremental cycle ergometer test to determine VO_{2peak}. Male participants began with a 3-minute warm-up at 60W (61). After the warm-up, the test started at 100W and increased by 30W every minute until exhaustion (33, 61). A participant's VO_{2peak} was determined as the highest 30-second average VO₂ value (33, 61). All participants had a 1-hour rest period before the 16-km familiarization time-trial. *Visit 3.* Each participant completed two 8-minute constant-load exercise bouts, one at moderate intensity and another at submaximal intensity, and had a 1-hour rest period before the 16-km time-trial. After visit 3, participants were randomly assigned to either an IMT or a sham-IMT (control) group using a random number generator (1 = IMT, 2 = sham-IMT). Participants used a flow-resistive inspiratory muscle trainer (Pro2Fit, Smithfield, Rhode Island) in order to complete eight weeks of IMT, performed three times a week, prior to any exercise training that day. After 8 weeks of the IMT or Sham-IMT intervention, participants returned to the laboratory to repeat the PFTs, the EIB diagnosis via EVH, the familiarization time-trial, and the constant-load and performance time-trial post-IMT for *Visit 4* and *Visit 5*.

6.0 Study Procedures

All study procedures are being conducted for research purposes only.

Specific Measures:

Pulmonary function testing & EIB Diagnosis: Pulmonary function testing was performed in accordance with the American Thoracic Society (2, 8, 62, 63). Maximal expiratory flow-volume (MEFV) loops were assessed to determine the degree of EFL using a handheld computerized pneumotachograph spirometer before and after the eucapnic voluntary hyperpnea (EVH) challenge, and using a metabolic cart (Vmax Encore System; CareFusion, Yorba Linda, CA) before and after exercise testing. The test included a forced vital capacity (FVC) maneuver in order to determine the participants FEV₁, FVC, peak expiratory flow (PEF), forced expiratory flow after 25 and 75% of FVC (FEF_{25-75%}), and FEV₁/FVC. Prior to exercise testing, spirometry was performed in triplicate, selecting the three best maneuvers with FEV₁ within 0.15 L. Prior to the EVH challenge, participants completed five maneuvers, and the average of the three best maneuvers with FEV₁ within 0.15 L was analyzed (63).

The EVH challenge is used as a surrogate for an exercise challenge to diagnose EIB. After establishing a baseline FEV₁, the target ventilation rate was calculated (L/min) (FEV₁ × 30) and is maintained by the participant for 6 minutes while breathing dry air from a Douglas bag (5% CO₂, 21% O₂, balance N₂) (4, 10, 11, 64) through a two way non-rebreathing valve (Hans-Rudolph, Shawnee, KS). Spirometry was performed after completion of the EVH challenge to assess changes in FEV₁ at 5-minute intervals over 30 minutes (8, 30). Participants with ≥ a 10% drop in FEV₁ (eq. 1) were deemed to have tested positive for EIB (65). Severity is characterized into three categories: mild, moderate, and severe. Mild is indicated as ≥ 10%, and less than 25%, moderate is ≥ 25%, and less than 50%, and severe is ≥ 50%, according to the American Thoracic Society Guidelines (8, 13, 38, 64).

$$\text{Percentage Drop FEV}_1 = \left[\left(\frac{\text{FEV}_1 \text{ Baseline} - \text{lowest value FEV}_1 \text{ EVH}}{\text{FEV}_1 \text{ Baseline}} \right) \times 100 \right] \quad [1]$$

Inspiratory Muscle Training (IMT) & Sham-IMT Training: A flow-resistive IMT protocol, as described previously (26, 29, 30, 33-35), was used in this study. Participants used the Pro2Fit (Smithfield, Rhode Island) flow-resistive inspiratory muscle trainer to complete 8 weeks of IMT, performed three times a week with 24 hours between sessions, and did not perform any aerobic exercise training that day. The training device consists of a handheld unit interfaced with a tablet or smartphone via a wireless Bluetooth connection. The test of incremental respiratory endurance (TIRE) protocol requires users to exhale forcefully to residual volume and immediately inhale maximally (maximum inspiratory pressure, MIP) against a 2mm diameter leak, and sustain the inhalation until task failure. The area under the pressure-time curve generated by MIP is known as sustained maximal inspiratory pressure (SMIP). Participants were required to complete 3 SMIP maneuvers during each training session and use the best of the 3 for that day's training template (corresponding to about 80% SMIP) via the Pro2Fit software. Participants must match or exceed the SMIP template with each increasing

level of the work-rest ratio. Work at each level consists of 6 breaths, for a total of 36 breaths. If six breaths are completed, the next level starts. Rest intervals will progressively shorten as training continues, from 40 seconds to 30-, 20-, 15-, 10-, and 5-seconds. The training session is terminated if participants are unable to match at least 90% of the training template for two consecutive breaths or have completed all 36 breaths (25). The 30% SMIP used for the sham-IMT group has previously been shown not to elicit any training adaptations (26, 29, 30, 33-35). Compliance was assessed by summing the number of recorded sessions for each participant and dividing by the total number of prescribed sessions.

Constant Load & Time-Trial Cycling Exercise: Before exercise, the participant adjusted the seat height on the cycle ergometer (Velotron, Velotron® Racermate, Seattle, WA), and then were fitted with a facemask (Hans-Rudolph, Shawnee, KS) and flow probe connected to a metabolic cart (Vmax® Encore, Vyair Medical, Mettawa, IL) and a Polar HR Monitor (Polar, Helsinki, Finland) underneath the sternum. Each participant completed two constant-load (CL) exercises with a 5-minute rest period in between, one at 15% below the gas exchange threshold (GET; CL1) and another at 15% above the gas exchange threshold (CL2), corresponding to 85% $\text{VO}_{2\text{peak}}$ (42). Males warmed up for 5 minutes at 60W, followed by a 5-minute rest (42, 66). After the 5-minute rest period, participants cycled at 5W for 2 minutes, immediately followed by a predetermined moderate workload. The moderate and submaximal workloads are determined from their GETs, estimated from changes in breath values using the modified V-slope method (42). Each participant completed a familiarization time-trial (TT) to learn the cycle gearing system and to reduce any further learning effects (61, 67). The cycle ergometer recorded each participant's power output (PO), speed, and time to complete the time-trial (33). The ergometer allows participants to vary their resistance and power output, with an electronic gearing system during the 16-km TTs, simulating an actual performance scenario.

Ratings of exertional dyspnea & leg fatigue: During constant-load cycling and the cycling time-trial, three modified Borg scales (0-10) were placed at arm's length, comfortably reachable by the participant on the cycle ergometer. Participants were asked to indicate their ratings of perceived breathing intensity, 0 indicating "not noticeable" and 10 indicating "maximal intensity imaginable". Secondly, participants were asked to rate perceived breathing unpleasantness, with 0 indicating "not unpleasant" and 10 indicating "maximal unpleasantness imaginable". Lastly, participants were asked to rate leg fatigue, with 0 indicating "not fatigued at all" and 10 indicating "total fatigue and exhaustion". Ratings were recorded every 2 minutes during each of the 8-minute constant loads and every 4 km during the 16-km time-trial.

Femoral Blood Flow (FBF): The limb blood flow protocol for the femoral artery, as previously described (65, 68-72), was used in the study. With participants at rest on the cycle ergometer with their right leg straight and relaxed, femoral artery diameter (as internal diameter) and blood velocity were measured 2-3 cm proximal to the superficial/deep bifurcation with an ultrasound Doppler system in triplex mode (Aplio 300; Toshiba Medical Systems Corporation), equipped with a linear array transducer functioning at an imaging frequency of 7.5 MHz. Blood velocity (cm/s) will be assessed with an insonation angle $\leq 60^\circ$, with the sample volume maximized and centered in real

time according to vessel size and position. With participants in an upright position, blood velocity and vessel radius (cm) were measured at rest prior to the start of exercise and during the last 10 seconds of the first constant load (CL1) and the second constant load (CL2). LBF (mL/min) was calculated using Equation 2.

$$LBF = \left[\left((\text{mean blood velocity (cm/s)}) \times \pi (\text{vessel radius (cm)})^2 \right) \times 60 \right] \quad [2]$$

Near-infrared spectroscopy (NIRS): As described previously ([28](#), [73-75](#)), near-infrared spectroscopy (NIRS) optode holders and optodes (OxiMon MKIII; Artinis Medical Systems, The Netherlands) were placed on the vastus lateralis of the participant's right leg and over the right 6th intercostal space at the anterior axillary line to monitor the deoxygenation status of the respiratory and limb locomotor muscle. Limb optode placement was approximately 15cm above the patella and 5cm lateral from the thigh's midline. Placement locations were marked with a semi-permanent marker, and holders were positioned to the skin surface with double-sided tape and covered with a black elastic bandage wrap to limit extraneous light from influencing the probe and to limit movement during exercise. The system emits NIR light to the target tissue via fiber-optic cables at wavelengths of 760 and 850nm. Optode separation distance within the optode holder for the vastus lateralis and anterior axillary line was 4cm (40mm). Light emitted from the fibers is half or less than half the distance between the emitter and the detector, allowing a depth of tissue of approximately 1-2cm. Skinfold measurements of the right mid-axillary and right thigh region determined the depth of tissue. A differential pathlength factor (DPF) of 4 was used. Light reflected from the tissue is detected by a photomultiplier tube and is recorded at a sampling rate of 50Hz. Based on a modified Beers-Lambert Law, concentrations were estimated for deoxygenated ([HHb]) hemoglobin and myoglobin in tissue. Resting values were obtained when the participant was sitting on the ergometer with the legs relaxed. Respiratory and limb deoxygenation were measured during each constant load and cycling time-trial. The collected data were filtered using OxySoft (Artinis Medical Systems, The Netherlands) to smooth the raw data.

Flow Limitation: At specific points during the exercise bout, participants were instructed to perform an inspiratory capacity (IC) maneuver, inspire to total lung capacity (TLC), and then exhale back to breathing normally. Respiratory mechanical constraint was calculated by the tidal volume (V_T)/IC ratio to indicate the degree of dynamic hyperinflation, further implicating the potential of EFL ([56-60](#)). In conditions characterized by pronounced mechanical constraint (e.g., COPD), IMT can reduce diaphragm activation and dyspnea ([76-78](#)). In asthma/EIB, however, resting spirometry is typically preserved and dynamic hyperinflation becomes prominent only under severe obstruction or near-maximal ventilation ([44](#), [51](#), [79-81](#)). Given that V_T generally reaches a mechanical ceiling when ~70% of IC is used and inspiratory reserve volume (IRV) approaches ~0.5–1.0 L, dyspnea intensity closely tracks this V_T /IC ratio rather than inspiratory strength per se ([56-60](#)).

7.0 Study Withdrawal/Discontinuation

Participants can voluntarily withdraw from the study at any time by contacting any of the researchers on the study via any available means (personal contact, email, phone,

etc.). If a researcher on the project wishes to withdraw a subject from the study, they will contact the individual directly (personal contact, email, phone, etc.). Possible indications for withdrawal by a researcher include: Concern that a participant could injure themselves by performing on of the exercise tasks in the study, results that do not meet the criteria for inclusion in the study, an abnormal response to exercise, an inability to complete the exercise tests, inability of a participant to complete a task properly to obtain valid measures, etc.

8.0 Statistical Considerations

Data analysis was conducted using GraphPad Prism (GraphPad Software LLC, San Diego, CA, USA). All dependent variables were assessed for normality using the Shapiro-Wilk test, and corresponding Q-Q plots were visually inspected. When the assumption of normality was not met, a non-parametric Wilcoxon signed-rank test was performed. To evaluate main and interaction effects, a two-way repeated-measures ANOVA was performed for each outcome variable, with time (pre, post) and group (IMT, Sham-IMT) as within- and between-participants factors, respectively. When missing data precluded a full factorial ANOVA, a mixed-effects model with restricted maximum likelihood (REML) was used to account for unbalanced datasets and preserve statistical power. Significance was set at $p < 0.05$ for all comparisons. Data are reported as means \pm standard deviations (SD) and mean differences (MD) with 95% confidence intervals (CI).

A statistical power analysis was performed to estimate sample size using G*Power 3.1.9.7 (University of Kiel, University of Düsseldorf, and University of Mannheim, Germany). Utilizing F tests for ANOVA determined that 20 participants total (10 = IMT, 10 = Sham-IMT) are needed in the proposed study for a power of 0.80, with an effect size of 0.25 and an $\alpha = 0.05$. Based on previous work by Turner et al., (31), Duruturk et al., (46), Shei et al., (29), Hursh et al., (33), and Faghy et al., (82), standard parameters of $1-\beta = 0.8$ and $\alpha = 0.05$ are suggested. However, due to the limitation of participant recruitment, only 11 participants completed the study. Given the modest sample size, these findings should be interpreted as preliminary and hypothesis-generating. Given the modest and imbalanced sample size, statistical findings were interpreted with emphasis on effect sizes and 95% confidence intervals rather than sole reliance on p values. Interaction effects were considered the primary test of intervention efficacy, whereas within-group changes were interpreted descriptively to characterize response patterns. Non-significant findings were not interpreted as evidence of no effect but rather as inconclusive within the constraints of the present sample.

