3.0 Outcome Measures

3.1 Primary Outcome Measures

Outcomes of interest is the severity of exercise-induced bronchoconstriction (EIB), inspiratory muscle strength and endurance, and cycling performance.

EIB severity will be measured using the pre- and post-values of the percentage drop in forced expiratory volume in 1 second (FEV₁) obtained from the eucapnic voluntary hyperpnea (EVH) test before and after IMT.

Inspiratory muscle strength and endurance will be measured using the flow-resistive trainer device that will record maximum inspiratory pressure and sustained maximum inspiratory pressure for 8 weeks.

Cycling performance will be summarized by pre- to post-values in power output, time, and speed time to complete the time-trial and constant loads before and after IMT.

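### Normality is checked on the raw outcomes rather than on within-arm change, so the 10% entry cut can by itself trigger a fallback test with no group term for Aim 1a

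*Combined protocol and SAP*

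**What the plan says.** Section 8.0 (Statistical Considerations) describes the check: "All dependent variables were assessed for normality using the Shapiro-Wilk test, and corresponding Q-Q plots were visually inspected". It then gives the consequence of failing: "When the assumption of normality was not met, a non-parametric Wilcoxon signed-rank test was performed". Neither sentence mentions residuals or change scores. Neither says whether pre, post, pooled or by-arm values were examined.

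The main analysis is a two-way repeated-measures ANOVA "with time (pre, post) and group (IMT, Sham-IMT) as within- and between-participants factors, respectively", which the section describes as applied to every outcome. On interpretation it says: "Interaction effects were considered the primary test of intervention efficacy, whereas within-group changes were interpreted descriptively".

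Three other sections bear on the point:
- Section 3.1 defines the first primary outcome: "EIB severity will be measured using the pre- and post-values of the percentage drop in forced expiratory volume in 1 second".
- Section 4.1 admits only people whose FEV₁ falls by 10% or more after EVH.
- Section 5.0 says that at Visit 1 participants "completed a eucapnic voluntary hyperpnea (EVH) challenge to diagnose EIB". It mentions a screening visit as well but describes no second pre-training EVH.

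**The concern.** A normality check that decides which test is used should look at the quantity whose normality that test needs. For the time-by-group interaction with two time points, this is the change within each arm. The shape of the raw outcome across people does not matter, because each person's level cancels in the change.

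For the percentage drop in FEV₁, the raw pre value is shaped by the entry rule. The same Visit 1 challenge supplies both the eligibility result and the baseline, so no pre value can lie below 10%. A check on that variable can fail because of who was admitted, while the ANOVA is sound.

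At stake is the randomised comparison for Aim 1a. The signed-rank test is a paired test without a group factor. An outcome handled only by that test keeps the within-group changes, which the plan treats as descriptive, and has no test of IMT against sham.

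**Working it through.** The plan gives no figure of its own for this check, so there is nothing to reproduce. The planned 20 and the 11 completers enter only as scenario sizes.

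**1. What the interaction needs.** Let D = post − pre for each participant. The interaction contrast is mean D (IMT) − mean D (sham). Its statistic is t = (D̄₁ − D̄₂) / [s·√(1/n₁ + 1/n₂)], where s is the pooled within-arm SD of D, and F(1, N−2) = t². The residual degrees of freedom are 20 − 2 = 18 as planned and 11 − 2 = 9 for the completers. The normality assumption concerns D within arm.

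**2. Inputs.**
- From the documents: entry at a drop of 10% or more; significance level 0.05; 10 per arm planned; 11 completers.
- Assumed, because the documents give no mean, SD, correlation or arm split: a normal true drop with the means and SDs in the table; visit-to-visit SD 4 points; a true IMT effect of 7 points; a 6/5 split of the completers; Shapiro-Wilk applied mechanically at 0.05; and a failed check removing the outcome from the ANOVA.

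Each scenario was simulated 2,000 times. Pre = true drop + error, kept only if at least 10. Post = true drop + new error, minus the effect in the IMT arm.

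**3. Results.** Interaction power is 76–78% at N = 20 and 46–49% at N = 11. Loss is that range minus the chance that the interaction is both run and significant.

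| Mean, SD of true drop | Raw pre fails, N=20, no effect | Run and significant, N=20 | Loss (points) | Run and significant, N=11 | Loss (points) |
|---|---|---|---|---|---|
| 20, 8 | 14% | 64% | 12–14 | 41% | 5–8 |
| 15, 6 | 26% | 56% | 20–22 | 40% | 6–9 |
| 12, 7 | 38% | 47% | 29–31 | 37% | 9–12 |
| 8, 8 | 49% | 38% | 38–40 | 36% | 10–13 |
| 5, 8 | 59% | 32% | 44–46 | 32% | 14–17 |

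Repeat simulations put the lowest run-and-significant figure at N = 20 at 31%, so the largest loss there is 78 − 31 = 47 points. Over repeats and the variant in step 4, raw pre or post fails in about 11–35% of trials at N = 11. At N = 20 the range is about 16–61%. Change residuals fail in about 4–6%.

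**4. Sensitivity to the assumed distribution, N = 11.** This variant draws pre values from a normal distribution with SD 8, cut at 10, with pre–post correlation 0.5–0.9.
- Mean 5 to 15: pre fails in about 12–30% of trials, pre or post in 16–35%, and change residuals in 4–5%.
- Mean 25: pre fails in 4–5% and pre or post in 8–10%, so the cut hardly matters.
- No cut at all: pre fails in about 5% and pre or post in about 9%. Part of every pre-or-post figure is therefore just the cost of testing twice.
- Log-normal parent (median 12, log-SD 0.6): pre or post fails in 63–68% of trials. Change residuals also fail in 12–15%, so they are not always near-normal.

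**5. Where the loss arises.** Keep the raw-variable check but send failures to a rank-sum test on change. Power at N = 20 then moves from 76–78% to 74–76%, a loss of at most about 3 points. At N = 11 the loss is at most about 4 points. Nearly all of the loss in step 3 therefore comes from the missing group term. The signed-rank test is also weak here even as a within-arm test: its smallest two-sided p is 2/2⁵ = 0.0625 in an arm of 5 and 2/2⁶ = 0.031 in an arm of 6.

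**The case against.** The strongest reply is that the diversion is inferred. Section 8.0 describes the ANOVA as applied to every outcome and does not say that a failed check removes one. The signed-rank test could be a within-group supplement, in keeping with the descriptive role given to within-group changes. On that reading the interaction is always available. This stands as a genuine alternative, although the wording that a different test was performed when normality failed points more naturally to replacement.

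Second, the sentence on normality may be shorthand. It does not exclude a residual check, and it pairs Shapiro-Wilk with visual inspection of Q-Q plots, which a mechanical cut at 0.05 does not model. This also stands, and one clarifying sentence would settle it.

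Third, the scenarios lean towards low means. With total SD √(8² + 4²) = 8.94, means of 5 and 8 imply that about 71% and 59% of candidates would fail the entry test, in a group already treated and prescribed SABAs. That is a fair reason not to rely on the upper end of the ranges.

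Fourth, a residual-based gate would itself cost about 2 points, so the net loss at 11 completers from checking the wrong quantity is nearer 4–14 points.

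Finally, the plan calls its findings preliminary and stresses effect sizes and intervals over p values. That softens a loss defined by significance. It does not supply the between-arm estimate, which comes from the analysis that may be bypassed.

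**Conclusion.** The point holds as a risk created by the written rule. The check is applied to the wrong quantity for the stated efficacy test, and the entry criterion can make it fail for the first primary outcome. If failure means replacement, Aim 1a loses its IMT-versus-sham test. At the 11 completers, the raw pre-or-post check fails in about 11–35% of trials against about 4–6% for change residuals, and the chance that the interaction is run and significant falls by about 5–17 points. These figures rest on assumed means of 5–20, SDs of 6–8, a visit-to-visit SD of 4, a 7-point effect and a 6/5 split. With a mean near 25 the effect is small.

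A reader might infer three stronger things that the documents do not support:
- **That the FEV₁ outcome was in fact dropped from the efficacy test.** No result of the check is given, and replacement is not stated.
- **That truncation makes failure likely.** Under a normal parent it happens in a minority of trials at 11 completers.
- **That the 12–47 point loss applies to this trial.** It belongs to the planned 20.

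Nor is the trigger the main source of harm. With a between-group fallback on change, it would cost only a few points.

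**What to change.** In Section 8.0, replace the sentence on normality with one saying that normality is assessed on the model residuals, equivalently on post-minus-pre change within each arm. Add that the IMT-versus-sham comparison of change, with its 95% CI, is reported for every outcome whatever the check shows. Any non-parametric analysis should be a between-group test on change, such as a rank-sum or permutation test, and be labelled a sensitivity analysis. If residuals were in fact checked, or the signed-rank test only supplemented the ANOVA, say so.

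The cost is two or three sentences and a re-run on existing data. The one downside is extra analysis and reporting for any outcome already moved to the signed-rank test.

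### For non-normal outcomes the plan names only a paired signed-rank test, which cannot compare IMT with sham

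*Combined protocol and SAP*

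**What the plan says.** Section 5.0 sets the design: "The study design is a randomized, single-blind parallel group study". The question is therefore IMT against sham.

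Section 8.0 then gives these rules:

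- All dependent variables are checked with Shapiro-Wilk and by looking at Q-Q plots. "When the assumption of normality was not met, a non-parametric Wilcoxon signed-rank test was performed".
- The main model treats time as a factor within participants and group as a factor between them: "To evaluate main and interaction effects, a two-way repeated-measures ANOVA was performed for each outcome variable".
- On what counts as evidence of efficacy: "Interaction effects were considered the primary test of intervention efficacy, whereas within-group changes were interpreted descriptively to characterize response patterns".
- On the threshold: "Significance was set at $p < 0.05$ for all comparisons". Whether tests are one- or two-sided, and exact or approximate, is not stated.
- "only 11 participants completed the study", and the section calls the sample imbalanced without giving the split.

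No between-arm rank or permutation method appears anywhere. The text does not say whether the signed-rank test replaced or accompanied the ANOVA, or whether it was run in each arm or on everyone together.

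**The concern.** The test the plan relies on for efficacy and the test it names for non-normal data answer different questions. The interaction asks whether the pre-post change differs between arms. The signed-rank test asks whether the change in a single set of people is centred on zero. Run per arm, it compares each arm with itself; run on all completers, it tests time. Neither uses the sham arm as a control.

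This matters most where both arms may change together. Entry requires an FEV₁ fall of at least 10% at EVH (section 4.1). The visit 1 EVH appears to be the only one before training (section 5.0), so regression to the mean could lower the measured fall in both arms. Section 6.0 itself recognises learning effects in the time trials. Some outcomes could also plausibly fail a normality check: the EVH fall is truncated at entry, and dyspnea and leg fatigue are bounded 0–10 ratings.

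**Working it through.** The plan gives no figure for this test, so there is none to reproduce. The planned total of 20 plays no part below.

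**Inputs.** From section 8.0: 11 completers, unequal arms, threshold 0.05. Assumed: exact two-sided tests, no ties or zeros, and splits of 6/5, 7/4 and 8/3.

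**1. What each test can see.** With two time points, the interaction is a comparison of mean change between arms. The signed-rank statistic uses only the signs and ranks of the changes in the sample it is given. Group membership does not enter.

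**2. Smallest attainable p, per arm.** With 11 people in two arms, at least one arm has 5 or fewer. The smallest exact two-sided signed-rank p is 2/2ⁿ:

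- n = 3: 2/8 = 0.25
- n = 4: 2/16 = 0.125
- n = 5: 2/32 = 0.0625
- n = 6: 2/64 = 0.031
- n = 11 (pooled): 2/2048 = 0.001

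An arm of 5 or fewer therefore cannot reach 0.05 on an exact two-sided test. The limit does not apply to a pooled run. At n = 5 it also fails if the test is one-sided (1/32 = 0.031) or uses the normal approximation without continuity correction (about 0.043; 0.059 with the correction).

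**3. What happens if a signed-rank p is read as efficacy.** Changes were simulated as normal with equal SD and no true IMT-sham difference, with IMT the larger arm. The common pre-post change is in units of the SD of change (40,000 runs per cell).

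| Common change | IMT significant, sham not: 6/5 | 7/4 | 8/3 | Pooled test significant | Interaction test |
|---|---|---|---|---|---|
| 0 | 3% | 5% | 4% | 4% | 5% |
| 0.5 SD | 11% | 19% | 19–20% | 29% | 5% |
| 1 SD | 36% | 56% | 61% | 81% | 5% |

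A repeat with 200,000 runs agreed to within a percentage point. If IMT has 5 or fewer, the pattern occurs in 0% of trials, because that arm cannot reach significance. The interaction test stays at 5% throughout.

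**4. Whether a between-arm rank test is feasible.** The smallest exact two-sided Mann-Whitney p on change scores is 2/C(11, n₁): 2/462 = 0.004 (6/5), 2/330 = 0.006 (7/4) and 2/165 = 0.012 (8/3). At 9/2 it is 2/55 = 0.036. Only at 10/1 (2/11 = 0.18) could it not reach 0.05.

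**The case against.** The best defence is that nothing was replaced. The plan says the ANOVA was run for each outcome, so the signed-rank test may be an added within-group check. The plan also calls within-group changes descriptive and treats non-significant results as inconclusive. As to p values, "Given the modest and imbalanced sample size, statistical findings were interpreted with emphasis on effect sizes and 95% confidence intervals". Normality was judged partly from Q-Q plots, not from Shapiro-Wilk alone.

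Much of this stands. A reader might infer that any outcome sent to the signed-rank test gets a wrong efficacy answer, that a spurious IMT-only result arises by construction, or that a real IMT effect could never be declared. The documents do not support those readings. Under the plan's own rules, such an outcome has no efficacy test rather than a wrong one. The IMT-only pattern depends on a common change and on a split that is not reported. The small-arm limit depends on an exact, two-sided, per-arm test that is not specified. Section 6.0 also says the sham load was previously shown not to produce training adaptations and that a familiarization trial was used to reduce learning. Both make a large shared change less likely, though neither excludes it. Nor do the documents show that any outcome was in fact analysed this way.

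The gap remains. A test performed only when normality fails is most naturally a substitute. If it is a supplement, the between-arm comparison still rests on an ANOVA whose assumption has been judged unmet, with no alternative named. And a 0.05 threshold for all comparisons invites reading the signed-rank p as a result.

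**Conclusion.** The point holds as a mismatch between the named efficacy test and the named non-parametric method. For outcomes judged non-normal, the plan provides either no test of IMT against sham or only one whose normality assumption it has judged unmet.

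The harm is conditional. It arises if a signed-rank p is taken as evidence of efficacy, and its size runs from negligible with no shared change to large with a shared change of 1 SD. Those rates assume normal changes with equal SD, although it is non-normal data that would trigger the rule, so they illustrate the mechanism and do not estimate an error rate for this trial.

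**What to change.** State whether the signed-rank test replaced or supplemented the ANOVA, and whether it was run per arm or pooled. Then replace the sentence with wording such as:

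> Where the model's residuals (or change scores) show material non-normality, IMT and sham are compared by an exact Mann-Whitney or permutation test on the pre-post change, with the Hodges-Lehmann between-group difference and 95% CI.

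Label any signed-rank result as descriptive and within-group only, report the split of the 11 completers, and re-run the affected outcomes. Running the rank test for every primary outcome as a sensitivity analysis is optional. The cost is a change of wording and a small re-analysis of existing data.
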